## 10.3 Statistical Analyses

The statistical analysis plan will be developed and finalized before database lock and will describe the selection of participants to be included in the analyses, and procedures for accounting for missing, unused, and spurious data. Below is a summary of planned statistical analyses of the primary and secondary endpoints.

A description of the participant population will be included in a statistical output report, including subgroups of age, gender, and race.

## 10.3.1 Efficacy Analyses

The main efficacy analyses will be performed on the efficacy population for the final analysis. Efficacy analyses based on the response-evaluable population may be performed for interim analyses (as per Section 10.3.8). Efficacy analyses may be performed on selected subgroups, including biomarker-selected subgroups. Efficacy analyses will be performed using the RECIST v1.1 criteria. Additional details on efficacy analyses are provided in Table 10.3.1-1.

Table 10.3.1-1: Part 1 Efficacy Analysis

Endpoint	Statistical Analysis Methods
ORR is defined as the proportion of participants whose BOR is either CR or PR in the population of interest.	Estimate of ORR and corresponding two-sided exact 95% CI using the
BOR for a participant will be assessed per RECIST v1.1 by investigator, otherwise specified	treatment for each tumor type
DOR  DOR for a participant with a BOR of CR or PR, is defined as the time between the date of first response and the date of the first objectively documented tumor progression per RECIST v1.1 or death, whichever occurs first.	Median duration of response using and corresponding two-sided 95% CI using Brookmeyer and Crowley methodology (using log-log transformation) by treatment for each tumor type

Abbreviations: BOR, best overall response; CI, confidence interval; CR, complete response; DOR, duration of response; ORR, objective response rate; PR, partial response; RECIST, Response Evaluation Criteria in Solid Tumors.

Table 10.3.1-2: Part 2 Efficacy Analysis

The approach to handling events such as subsequent cancer

therapy will be consistent between ORR and DOR.

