#### **OVERALL RATIONALE FOR PROTOCOL AMENDMENT 07**

This protocol amendment updates the primary analysis for the randomized assessment in Part 2. Additional analysis on baseline serum IL-8 (sIL-8) data suggested an association with tumor burden, decreasing the relevance of using sIL-8 as a selection biomarker. Thus, the primary analysis population was changed from to all randomized participants. To facilitate a timely analysis, the primary endpoint was further revised to objective response rate (ORR). Approximately participants (in each treatment arm) currently enrolled in Part 2 will provide a sufficient sample size to analyze the new primary endpoint of ORR under a statistical framework

Additionally, for Part 2,

objectives and endpoints no longer considered essential for the study analysis have been reclassified as exploratory.

Additional changes are made to simplify study procedures for participants following the final analysis. These changes aim to alleviate participant and site burden and remove sample collections and study procedures that are no longer considered necessary. Assessments and procedures deemed necessary for monitoring the safety of the subjects remain unchanged.

SUMMARY OF KEY CHANGES FOR PROTOCOL AMENDMENT 07		
Section Number & Title	Description of Change	Brief Rationale
Title Page	Updated the clinical scientist and clinical trial physician/medical monitor information.	Administrative change.
	Removed the EudraCT identifier and updated the European Union trial number.	The term "EudraCT" is obsolete, as it refers to the previous European legislation.
Section 1: Protocol Summary	Updated to reflect changes made in the body of the protocol.	To align with protocol updates.

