# 4 OBJECTIVES AND ENDPOINTS

Table 4-1: Objectives and Endpoints - Part 1

Objectives	Endpoints
Primary	
To characterize safety, tolerability, and DLTs, and to determine the RP2D of BMS-986253 administered in combination with nivolumab, or in combination with nivolumab and ipilimumab in participants with advanced solid tumors.	Incidence of AEs, SAEs, AEs meeting protocol- defined DLT criteria, and AEs leading to discontinuation, death, and laboratory abnormalities.
Secondary	

 
To evaluate the preliminary efficacy of BMS-986253 in combination with nivolumab in participants with advanced solid tumors using RECIST v1.1.
 
To characterize the PK and immunogenicity of BMS-986253 when administered in combination with nivolumab, or in combination with nivolumab and ipilimumab in participants with advanced solid tumors.
 
To assess serum IL-8 levels at baseline (ie, screening) and changes in IL-8 levels on treatment.
 
	
 
ORR and DOR per RECIST v1.1 per investigator.
 
Summary measures of PK parameters and incidence of ADA to BMS-986253.
 
Summary measures of IL-8 and change (or percent change) from baseline in IL-8 on treatment.
 

Abbreviations: ADA, anti-drug antibody; AE, adverse event; DLT, dose-limiting toxicity; DOR, duration of response; EOT, end of treatment; ORR, objective response rate; PK, pharmacokinetic(s);

Protocol Amendment No.: 07

RECIST, Response

Evaluation Criteria in Solid Tumors; RP2D, recommended Phase 2 dose; SAE, serious adverse event.

[figure not shown]
Table 4-2: Objectives and Endpoints - Part 2

	Objectives	Endpoints
Pri	imary	
•	To compare the ORR of BMS-986253 plus nivolumab plus ipilimumab with placebo plus nivolumab and ipilimumab using RECIST v1.1.	ORR based on BICR assessments per RECIST v1.1 in all randomized participants.
Sec	condary	
•	To estimate PFS of BMS-986253 plus nivolumab plus ipilimumab and placebo plus nivolumab and ipilimumab in participants with advanced melanoma using RECIST v1.1 (regardless of baseline serum IL-8 levels).	mPFS and PFS hazard ratio based on BICI assessments per RECIST v1.1.
•	To compare the safety of BMS-986253 plus nivolumab plus ipilimumab with placebo plus nivolumab plus ipilimumab in participants with advanced melanoma.	discontinuation, death, and laborator

Protocol Amendment No.: 07

Date: 17-May-2024 68

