# 5.4.3 Rationale for Selecting Participants Based on Serum IL-8

[figure not shown]
In healthy subjects, IL-8 is not typically present in the serum; however, it can be found in the serum of patients with various cancer types.

Protocol Amendment No.: 07

In Part 1C and in Part 2, participants will not be selected based on serum IL-8. The main purpose of Part 1C will be generation of safety data on the combination of BMS-986253 plus nivolumab plus ipilimumab, to support a randomized evaluation of BMS-986253 plus nivolumab plus ipilimumab versus placebo plus nivolumab plus ipilimumab in Part 2. In Part 2, the primary endpoints will be in all randomized participants regardless of baseline serum IL-8 level.

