# 10.2 Populations for Analyses

Population	Description	
Enrolled/Randomized	All participants who have signed informed consent and are registered into the IRT	
Treated	All participants who received at least 1 dose of study treatment	
Efficacy	All participants who take at least 1 dose of their planned full combination treatment.	
Response-evaluable	All treated participants with measurable disease at baseline and one of the following: (1) at least 1 post-baseline tumor assessment, (2) clinical progression, or (3) death	
Pharmacokinetic	All treated participants who have evaluable concentration-time data	

Population	Description
Immunogenicity	All treated participants who have baseline and at least one post baseline immunogenicity assessment
Biomarker	All treated participants with available biomarker data

Abbreviation: IRT, Interactive Response Technologies.

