# 10.3.8 Interim Analyses

#### 10.3.8.1 Part 1

Interim analyses will be performed for administrative purposes or publication. No formal inferences requiring any adjustment to statistical significance level will be performed.

Date: 17-May-2024

Approved v 8.0 930120018 9.0

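### The protocol gives two analysis sets for the Part 2 primary ORR: all randomized participants, and only those dosed with the full combination

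*Combined protocol and SAP*

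**What the plan says.** Three places in the current protocol text give the set for the Part 2 primary endpoint. Table 2 of the Protocol Summary and Table 4-2 of Section 4 both read "ORR based on BICR assessments per RECIST v1.1 in all randomized participants". Section 5.4.3 says "In Part 2, the primary endpoints will be in all randomized participants regardless of baseline serum IL-8 level". The rationale for Amendment 07 states the same intent: "the primary analysis population was changed from to all randomized participants" (the former population has been removed from the public text).

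Section 10.3 introduces the statistical text with "Below is a summary of planned statistical analyses of the primary and secondary endpoints". Section 10.3.1 then opens with "The main efficacy analyses will be performed on the efficacy population for the final analysis". Section 10.2 defines the Efficacy population as "All participants who take at least 1 dose of their planned full combination treatment". The Part 2 efficacy table, Table 10.3.1-2, sits in the same section, but its ORR row does not name the denominator.

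**The concern.** Being randomized carries no dosing condition. Membership of the Efficacy population does. The two sets therefore differ by definition, and they are attached to the same primary comparison.

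If Section 10.3.1 were followed for Part 2, some participants would leave the primary analysis because of something that happened after randomization. They need not be only the never-dosed: the definition asks for the full combination, and Section 7.6.6 allows dosing to stop at a visit, or for good, after an infusion reaction. A participant who received only part of the first combination could then be left out. Only the all-randomized set is free of this selection. The denominator of a randomized primary test should also not be open to choice between two written rules once treatment codes are known.

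**Working it through.** **1. The statements side by side**

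| Place | Set for the analysis | Limited to one part? |
|---|---|---|
| Table 2 and Table 4-2 | All randomized | Part 2 primary endpoint |
| Section 5.4.3 | All randomized, any baseline IL-8 | Part 2 |
| Amendment 07 rationale | All randomized | Part 2 |
| Section 10.3.1, opening sentence | Efficacy population (dosed with full combination) | No |
| Table 10.3.1-2, ORR row | Not named | Part 2 |

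No visible sentence reconciles the fourth row with the first three.

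**2. Can the two sets differ in practice?** Section 7.4 allows randomization up to 3 days before the first dose, so a randomized but undosed participant is possible. The number should be small: the gap is short, Table 2-6 puts both nivolumab and ipilimumab on Day 1, and Section 7.5.2 makes Part 2 double-blind, so exclusion is unlikely to depend on arm. The visible part of Table 2-6 does not show the row for BMS-986253 or placebo.

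**3. Is the randomized set itself defined?** Not cleanly. Section 10.2 merges enrolled and randomized into one row, based on consent and IRT registration. Table 2-2 uses IRT to record screen failures, and Section 7.4 assigns an IRT number before randomization. Read literally, that row includes people who were never randomized.

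**4. How large could the effect be?** The plan gives no figure to reproduce: the Part 2 sample size and assumed rates are not visible. The following is an illustration. Assumed inputs: a 30% ORR over all randomized (Section 5.4.8 cites 29%, by irRECIST, and 31% from two other studies), and a share f excluded of 2% or 5%.

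With response rate r among the excluded, the ORR in the Efficacy population is (0.30 − f × r) / (1 − f).

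- Excluded are all non-responders (r = 0): 0.30/0.98 = 30.6%; 0.30/0.95 = 31.6%. Shift 0.6 or 1.6 points.
- Excluded respond at half the rate (r = 0.15, assumed): (0.30 − 0.003)/0.98 = 30.3%; (0.30 − 0.0075)/0.95 = 30.8%. Shift 0.3 or 0.8 points.

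Effect on the difference between arms:

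- Equal exclusion, no true effect: 0.
- Equal exclusion, assumed true difference of 15 points, excluded are non-responders: 0.15/0.98 = 15.3 points; 0.15/0.95 = 15.8 points.
- No true effect, 5% against 2% excluded: 0.30/0.95 − 0.30/0.98 = 0.97 points if r = 0; 0.3079 − 0.3031 = 0.48 points if r = 0.15.
- No true effect, 3% against 2% excluded: 0.30/0.97 − 0.30/0.98 = 0.32 points if r = 0; 0.16 points if r = 0.15.

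The reverse direction agrees. If 29% and 31% are taken as rates among the dosed, counting an undosed 2% as non-responders gives 0.29 × 0.98 = 28.4% and 0.31 × 0.98 = 30.4%. With 5% undosed the results are 27.6% and 29.5% (0.29 × 0.95 and 0.31 × 0.95).

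**The case against.** Three arguments say that there is no real conflict.

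*The Section 10.3.1 sentence belongs to Part 1.* The section goes on to say "Additional details on efficacy analyses are provided in Table 10.3.1-1", which is the Part 1 table. It also refers to Section 10.3.8 for interim analyses, whose only visible subsection is Part 1. The table of contents lists no other, and the Amendment 07 change summary calls the Part 2 interim section a former one. This reading is possible. But the population sentence carries no such limit, Section 10.3 presents the text as covering the primary endpoints, and Section 7.5.2 also speaks of the final analysis for Part 2. If the reading is right, the visible part of Section 10 names no set at all for the Part 2 primary test, and the same edit is needed.

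*Section 10.3.1 is a default that the endpoint definition overrides.* Only the primary endpoint in Table 4-2 names all randomized participants, and PFS and OS start at first dose, which fits a dosed default. No sentence states the override, however, and a rule for the main efficacy analyses is a poor candidate for one that skips the primary endpoint.

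*The answer may lie in text that cannot be seen.* This stands as a limit. The visible text of Section 10.1.3 stops after the randomization sentence, the ORR method in Table 10.3.1-2 is incomplete, and Section 10.3 leaves the selection of participants to an SAP that is not among the documents. The date of the mismatch is also uncertain. The visible Amendment 07 change entries list Section 10.1.3 and Table 10.3.1-2 but neither Section 10.2 nor the opening of Section 10.3.1. That suggests a missed update without proving one.

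**Conclusion.** The concern holds for the visible protocol text: two differing rules are written for the analysis set of the Part 2 primary ORR. The finding does not extend to which set will be used. All randomized is plainly the intended set, so the opening sentence of Section 10.3.1 is the one to align.

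The numerical effect is probably small: in the cases shown, up to 1.6 points on one arm's ORR and just under 1 point of false difference. Those figures rest on assumed exclusion of 2% to 5%, an assumed 30% ORR, and excluded participants who respond less often than the rest. A larger or more unequal exclusion would give more; no exclusion would give none. The reason to correct it is pre-specification of the primary comparison more than the expected bias.

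**What to change.** - In Section 10.3.1 and Table 10.3.1-2, state that the Part 2 primary ORR is analysed in all participants assigned by IRT to 2A or 2B, in the arm assigned.
- State that participants with no dose or no post-baseline tumor assessment count as non-responders. The ORR definition implies this, but it needs saying: Section 9.4 has central review read the scans of treated participants, and Table 10.3.1-2 starts best overall response at first dose.
- If the Efficacy-population sentence is meant for Part 1, limit it to Part 1.
- In Section 10.2, define the randomized set separately from the enrolled set.
- Carry the same set into the SAP, which Section 10.3 already requires to be final before database lock.
- Optionally, keep the Efficacy population as a Part 2 sensitivity analysis.

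The cost is protocol and SAP wording before database lock, with no new data or participants. The one downside is that the reported ORR may be slightly lower.

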#### Endpoint **Statistical Analysis Methods** BICR-assessed ORR will be used to compare ORR between 2 treatment groups. The ORR is defined as the proportion of participants whose BOR associated odds ratio and CI will also be is either CR or PR in the population of interest. calculated. BOR for a participant will be assessed per RECIST v1.1. BOR per RECIST v1.1 is defined as the best response designation recorded between the date of the first dose and the date of first objectively documented progression per RECIST v1.1 or the date of subsequent therapy, whichever occurs first. For participants who continue treatment beyond progression per RECIST v1.1 or begin subsequent therapy, the BOR should be determined based on response designations recorded up to the time of the initial progression or subsequent therapy, whichever occurs first. For participants without documented progression or subsequent therapy, all available response designations should contribute to the BOR assessment. DOR Median duration of response using method and corresponding two-sided 95% CI DOR for a participant with a BOR of CR or PR is defined as the time between the date of first response and the date of the first objectively documented tumor progression per RECIST v1.1 or death, whichever occurs first. Participants who die without a reported progression will be considered to have progressed on the date of their death. Participants who did not progress or die will be censored on the date of their last evaluable tumor assessment. Participants who did not have any on-study tumor assessments and did not die will be censored on the date of first dose. Participants who started any subsequent anticancer therapy, including tumor-directed radiotherapy and tumor-directed surgery, without a prior reported progression will be censored at the last evaluable tumor assessment prior to initiation of the subsequent anticancer therapy.

# Table 10.3.1-2: Part 2 Efficacy Analysis

BICR-assessed PFS	The estimate of the PFS hazard ratio between treatment groups will be calculated using a
PFS is defined as the time from first dose to the date of first objectively documented progression, per RECIST v1.1, or death due to any cause, whichever occurs first. Clinical deterioration in the absence of objectively documented progression per RECIST v1.1 is not considered progression for the purpose of determining PFS. Participants who die without a reported progression will be considered to have progressed on the date of their death. Participants who did not progress or die will be censored on the date of their last evaluable tumor assessment. Participants who did not have	stratified with treatment and stratification factors as covariates. A two-sided 95% CI for the hazard ratio will also be presented.  The PFS curves for each treatment group will be estimated using product limit method and will be displayed graphically. Median PFS with corresponding two-sided 95% CI in each treatment group will be computed via the log-log transformation method.
any on study tumor assessments and did not die will be censored on the date of first dose. Participants who started any subsequent anticancer therapy, including tumor-directed radiotherapy and tumor-directed surgery, without a prior reported progression will be censored at the last evaluable tumor assessment prior to initiation of the subsequent anticancer therapy. The PFSR at time T is defined as the probability that a participant has not progressed and is alive at time T following first dose.	PFS rates at fixed time points (eg, 3, 6, 9 months, depending on the minimum follow-up) will be presented along with their associated 95% CIs. These estimates will be derived from estimate and corresponding CIs will be derived based on for variance derivation and on log-log transformation applied to the survivor function.
OS  OS is defined as the time between the date of first dose and the date of death due to any cause. For participants that are alive, their survival time will be censored at the date of last contact date (or "last known alive date"). OS will be censored at the date of first dose for participants who were dosed but had no follow-up.	A 2-sided 95% CI for median OS in each treatment group will be computed via the log-log transformation method. OS rates at fixed time points (eg, 12 months, depending on the minimum follow-up) will be presented along with their associated 95% CIs. These estimates will be derived from estimate and corresponding CIs will be derived based on for variance derivation and on log-log transformation applied to the survivor function.

Abbreviations: BICR, blinded independent central review; BOR, best overall response; CI, confidence interval; CR, complete response; DOR, duration of response; ORR, objective response rate; OS, overall survival; PFS, progression-free survival; PR, partial response; RECIST, Response Evaluation Criteria in Solid Tumors.

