- Cohort 1B2: 1200 mg of BMS-986253 Q4W and 480 mg of nivolumab Q4W
- Cohort 1B3: 600 mg of BMS-986253 Q4W and 480 mg of nivolumab Q4W

Assignment into any dosing regimen arm may be suspended

In addition, up to 4 new dosing regimens assessing the combination of BMS-986253 and nivolumab may be initiated

Additional cohorts for alternate dosing regimens may include:

- Cohort 1B4: 2400 mg of BMS-986253 Q2W and 480 mg of nivolumab Q4W
- Cohort 1B5: 1200 mg of BMS-986253 Q2W and 480 mg of nivolumab Q4W
- Cohort 1B6: 3600 mg of BMS-986253 Q2W and 480 mg of nivolumab Q4W

[figure not shown]
For any dosing regimen evaluating a higher dose of BMS-986253 than previously explored, an initial 4-participant safety-lead with a 28-day DLT period will be required. Approximately participants will be dosed in the treatment arms. Additional exploration of a specific dosing regimen may be warranted in Part 1B, in which case additional participants will be assigned to that dosing regimen.

A maximum of approximately participants will be

[figure not shown]
dosed in Part 1A and Part 1B.

(Part 1B) will open.

Protocol Amendment No.: 07 Date: 17-May-2024

Protocol Amendment No.: 07

Protocol Amendment No.: 07

Date: 17-May-2024 72

Part 2: Double-blind Randomized Evaluation of BMS-986253 plus Nivolumab plus Ipilimumab versus Placebo plus Nivolumab plus Ipilimumab in Advanced Melanoma

Part 2 will begin after determination of the RP2D of BMS-986253 based on Part 1A and 1B data and generation of safety data on the triplet combination of BMS-986253 plus nivolumab plus ipilimumab in Part 1C.

Part 2 is a double-blind randomized evaluation of BMS-986253 plus nivolumab plus ipilimumab (2A) versus placebo plus nivolumab plus ipilimumab (2B) to evaluate the efficacy of BMS-986253 in participants with advanced melanoma who are refractory to anti-PD-(L)1 therapy.

This portion of the study will include participants with unresectable or metastatic melanoma (non-ocular), who had progression on or after anti-PD-(L)1 therapy, but have not been treated with prior anti-CTLA-4 therapy (see Section 6.1). Participants will be randomly assigned in a 1:1 ratio to 1 of 2 treatment arms:

[figure not shown]
- 2A: BMS-986253 + nivolumab + ipilimumab
- 2B: placebo + nivolumab + ipilimumab

During randomization, participants will be stratified by the following factors as described in Section 7.4: screening serum IL-8 level, and lactate dehydrogenase (LDH) levels.

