If PK, pharmacodynamic, and/or safety analyses indicate further assessment of a dosing regimen is not warranted and/or assessment of additional dosing regimens is indicated, then randomization will be stopped, and subsequent participants will be assigned sequentially to dosing regimens available at that time. If any dosing regimen evaluates a higher dose of BMS-986253 than previously explored, an initial 4-participant safety lead-in with a 28-day DLT period will be required. Approximately participants will be dosed in the dosing regimen(s) of interest. Additional exploration of a specific dosing regimen may be warranted, in which case a maximum of approximately additional participants will be assigned to a dosing regimen of interest in Part 1B. A maximum of approximately participants will be dosed in Part 1B.

Part 1C is a safety evaluation of BMS-986253 in combination with nivolumab and ipilimumab. Part 1C will begin once the DLT period is completed for Cohort 1B6 (BMS-986253 3600 mg Q2W + nivolumab 480 mg Q4W), and will enroll simultaneously with Part 1B. In Part 1C, participants

Protocol Amendment No.: 07 Date: 17-May-2024

Protocol Amendment No.: 07

#### Part 2

Part 2 will begin after determination of the RP2D from Part 1 and generating safety data on the triplet combination of BMS-986253 plus nivolumab plus ipilimumab in Part 1C. Part 2 is a double-blind randomized evaluation of BMS-986253 plus nivolumab plus ipilimumab versus placebo plus nivolumab plus ipilimumab and will be conducted to evaluate the efficacy of BMS-986253 in participants who are refractory to anti-PD-(L)1 therapy.

IRT will be used to track the enrollment number.

Once assigned a subject ID in IRT, participants that have met all eligibility criteria will be randomized through IRT (up to 3 days prior to C1D1). The following information is required prior to participant randomization:

- Participant subject ID
- Date of birth
- Gender
- Screening serum IL-8 level

• Screening LDH

Participants will be randomized in a 1:1 ratio to treatment and control arms. Three stratification factors will be used during randomization: screening

and screening LDH (≤ ULN or > ULN). Screening serum IL-8 data will be transferred directly from the analyzing laboratory to IRT. BRAF status and screening LDH must be entered in eCRF by the site.

Approximately participants will be randomized in Part 2.

The exact procedures for using the IRT will be detailed in the IRT manual.

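### Part 2 times PFS and OS from first dose and runs efficacy on a dosed-only population, although its primary endpoint is set in all randomized participants

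*Combined protocol and SAP*

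**What the plan says.** **Design and primary population.** Section 5.1 states: "Participants will be randomly assigned in a 1:1 ratio to 1 of 2 treatment arms". Table 4-2, the matching table in the Protocol Summary and Section 5.4.3 all place the Part 2 primary endpoint in every randomized participant, whatever the baseline serum IL-8. Under Section 7.4, eligible participants are "randomized through IRT (up to 3 days prior to C1D1"), so randomization and first dose are separate events.

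**Time origin.** In Table 10.3.1-2, "PFS is defined as the time from first dose to the date of first objectively documented progression", and "OS is defined as the time between the date of first dose and the date of death due to any cause". The PFS rate at a fixed time is also counted from first dose. Section 10.3.7 repeats the OS definition without limiting it to one part of the study.

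**Fallback censoring.** For PFS, participants who lacked "any on study tumor assessments and did not die will be censored on the date of first dose". For OS the rule reads: "OS will be censored at the date of first dose for participants who were dosed but had no follow-up".

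**Best overall response.** It is "the best response designation recorded between the date of the first dose and the date of first objectively documented progression", or the start of subsequent therapy if that comes earlier.

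**Analysis population.** Section 10.3.1 assigns the main final efficacy analyses to the efficacy population. Section 10.2 limits that population to participants who received the whole planned combination at least once. The enrolled/randomized population in Section 10.2 is defined by consent and IRT registration and does not mention randomization. The ORR row in Table 10.3.1-2 leaves its population unspecified.

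**The concern.** A randomized comparison is protected by analysing people as randomized, from the moment of randomization. Part 2 departs from this in two places.

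First, a participant randomized but not dosed has no start date for PFS or OS. The fallback rules do not help, because they censor at a date that does not exist for that person, and the OS rule is expressly limited to those dosed. The PFS hazard ratio can therefore rest on a different set of people from the primary endpoint.

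Second, the population named in Section 10.3.1 excludes the undosed from ORR as well. It also excludes anyone who started treatment but never received every component of the assigned regimen. Two readers could compute the primary ORR with different denominators and each cite the protocol.

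**Working it through.** The point is definitional. The Part 2 sample size, alpha, power and target effect are not visible in the public text, so there is no plan figure to reproduce. The check follows one randomized, undosed participant through each rule and then gauges the scale under stated assumptions.

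**Step 1: the rules applied to a randomized, undosed participant**

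| Rule | Source | Result |
|---|---|---|
| PFS and PFS-rate origin | Table 10.3.1-2 | No start date |
| PFS censoring without assessment or death | Table 10.3.1-2 | Refers to a first-dose date that does not exist |
| OS origin | Table 10.3.1-2, Section 10.3.7 | No start date |
| OS censoring without follow-up | Table 10.3.1-2 | Covers dosed participants only |
| Best-response window | Table 10.3.1-2 | No responses recorded; the person can still be counted as a non-responder |
| ORR denominator, objectives | Table 4-2, Section 5.4.3 | Included |
| ORR denominator, analysis | Sections 10.2 and 10.3.1 | Excluded |

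The gap is in PFS and OS. For ORR, the conflict lies between the last two rows and does not come from the time origin.

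**Step 2: shift for dosed participants**

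The planned gap is at most 3 days, or 3 / 30.44 = 0.10 month. As a share of an assumed median PFS:

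- 2.8 months: 3 / (2.8 × 30.44) = 3 / 85.2 = 3.5%
- 4 months: 3 / (4 × 30.44) = 3 / 121.8 = 2.5%
- 6 months: 3 / (6 × 30.44) = 3 / 182.6 = 1.6%

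**Step 3: ORR under the two populations**

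With r responders, n randomized and u undosed non-responders in an arm, ORR is r/n on all randomized and r/(n − u) on dosed only. Assume 60 per arm and a 30% ORR, close to the 29% and 31% cited in Section 5.4.8:

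- u = 0: 18/60 = 30.0%
- u = 1: 18/59 = 30.5%
- u = 2: 18/58 = 31.0%
- u = 4: 18/56 = 32.1%

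Across 40 to 100 per arm and 1 to 4 undosed, the rise runs from 0.3 points (30/99 against 30/100) to 3.3 points (12/36 against 12/40).

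For the odds ratio, assume 24/60 against 18/60 responders:

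- All randomized: (24/36) / (18/42) = 1.56
- 3 undosed dropped from the experimental arm only: (24/33) / (18/42) = 1.70
- 3 dropped from control only: (24/36) / (18/39) = 1.44
- 3 dropped from each: (24/33) / (18/39) = 1.58

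The odds ratio moves noticeably only if the undosed fall unevenly between arms.

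**The case against.** **The time origin does not touch the primary endpoint.** A reader might infer that starting the best-response window at first dose drops undosed participants from ORR. The documents do not support that. ORR is a proportion, and someone with no response recorded can stay in the denominator as a non-responder. Exclusion from ORR comes only from the population named in Section 10.3.1. This objection stands.

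**First dose is a coherent choice.** The Part 2 scan schedule and the minimum duration for stable disease both run from first dose, and a dosed-only analysis is a recognised option under blinding. A reader might also assume that the origin was carried over from Part 1, but the Part 1 efficacy table has no PFS or OS row. The choice is consistent with the efficacy population. It is not consistent with an all-randomized primary endpoint, and the plan states both.

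**Moving the origin recovers little.** A participant censored at time zero is never at risk at an event time, so adds nothing to the PFS curve or the hazard ratio. Sections 5.1.6 and 9.4 limit central review to treated participants, so an undosed participant would add information mainly through a death. This also stands: the change should not be described as recovering everyone without loss.

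**The consequence is limited.** The PFS objective is one of estimation, the visible OS methods give per-arm medians and rates, and Section 5.1.5.3 ends survival follow-up. With blinded allocation and dosing planned within 3 days, the undosed are probably few and unrelated to arm.

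**The SAP may settle it.** Section 10.3 leaves participant selection and missing data to a SAP, whose text is not in the material reviewed. It could supply the rule, but the protocol would still contradict itself.

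**Conclusion.** The point holds as a minor inconsistency. Part 2 PFS, PFS rates and OS are undefined for anyone randomized and not dosed, and Sections 10.2 and 10.3.1 contradict the all-randomized population set for the primary ORR. The population conflict matters more, because it concerns the primary endpoint.

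The size is probably small. The time shift is at most about 3 days if first dose follows randomization as planned. The ORR figures rest on assumed arm sizes, an assumed 30% response and 1 to 4 undosed per arm; the documents give no undosed count, and it may be zero. The text does not show that the comparison is biased. It shows that the analysis set and the time origin do not match the randomized design.

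**What to change.** For Part 2 only:

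1. In Table 10.3.1-2 and Section 10.3.7, time PFS, PFS rates and OS from the date of randomization.
2. Censor at randomization those with no tumor assessment and no death for PFS, and those with no follow-up for OS.
3. In Section 10.2, define an all-randomized population by the act of randomization, and name it in Section 10.3.1 as the Part 2 efficacy population. A dosed-only analysis can remain as a sensitivity analysis.
4. State that randomized participants without a post-baseline response assessment, including the undosed, count as ORR non-responders. With that rule the best-response window can stay as it is.

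Part 1 definitions and the scan schedule need no change. The cost is wording in the protocol and SAP, to be settled before database lock. The randomization date is generated when IRT randomizes the participant, so no new data are needed.
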